1.0 Objectives

1.1 Primary Objective

- To assess the overall response rate (ORR) related to the combination of sorafenib + pembrolizumab in advanced hepatocellular carcinoma patients.

1.2 Secondary Objective

- To assess time to tumor progression in patients who received the combination therapy of sorafenib + pembrolizumab compared to historical data on sorafenib only treatment in patients with advanced hepatocellular carcinoma.

1.3 Exploratory Objectives

- To obtain data on changes in immune cell function and in the tumor microenvironment pre- and post-treatment to screen for potential biomarkers that may be able to predict clinical benefit.
- All patients will be followed for survival.

2.0 Background

Hepatocellular cancer (HCC) is a lethal malignancy and an increasing global health problem. With an estimated global incidence of 782,451 cases in 2012, it is the fifth-most common cancer and the sixth-most fatal.(1) HCC is a complex and heterogeneous tumor driven by angiogenesis and several genomic alterations including aberrant activation of signal transduction pathways such as EGFR, Ras/Erk, PI3K/mTOR and apoptotic signaling.(2)

2.1 Hepatocellular Carcinoma and Sorafenib

Sorafenib is a synthetic compound targeting growth signaling and angiogenesis. Sorafenib blocks the enzyme RAF kinase, a critical component of the RAF/MEK/ERK signaling pathway that controls cell division and proliferation. Sorafenib has an antiangiogenic effect by targeting vascular endothelial growth factor receptor-2/-3 (VEGFR-2/-3) and platelet derived growth factor receptor-beta (PDGFR-beta) tyrosine kinases, FLT3 Ret and c-Kit.

Targeting angiogenesis with agents such as the tyrosine kinase inhibitor sorafenib is now the standard of first line therapy for advanced HCC, but treatment is not curative and survival of these patients remains less than one year. Agents with a similar mechanism of action have not proven to be superior or more tolerable than sorafenib. There is a clear unmet urgent need for tolerable, effective therapies for advanced HCC.

2.2 Hepatocellular Carcinoma and Immune Dysfunction

Presently there are no validated biomarkers that predict response to sorafenib in HCC or other malignancies where the drug is approved for use.(3) As trial eligible patients are few, rationally designed, biomarker driven studies are urgently needed.

Since immune dysfunction from advanced cancer and hepatitis are hallmarks of HCC, new agents that target immune suppression are a major focus of HCC research. Studies from our laboratory on peripheral blood samples from HCC patients show that: (1) programmed cell death-1 (PD-1)+ T cell numbers and T cell PD-1 expression levels are elevated; (2) frequency of PD-1+ T cells and T cell PD-1 expression levels decreased in a patient with spontaneous HCC regression; (3) depletion of Tregs, MDSCs, and PD-1+ cells results in complete restoration of

Roswell Park Protocol No.: I 35316

HCC patient effector T cell granzyme B production in vitro.(4, 5) Others have shown that elevated cognate inhibitory molecule PD-1-ligand 1 (PD-L1) expression in HCC is associated with tumor aggressiveness and enhanced risk for postoperative recurrence.(6) Collectively, these observations support the rationale that immunotherapy may have therapeutic benefit in HCC.

Our laboratory has also studied whether sorafenib may impact the systemic immunological function in addition to its mechanism of action in the tumor and vasculature. Sorafenib targets multiple tyrosine kinase receptors, including Flt3 which is present on MDSC and Tregs.(7, 8) Multiple avenues for tumor-induced immunosuppression exist in HCC, including accumulation of MDSC and Tregs. Depletion or inhibition of these cells is considered an important clinical feature for successful immunotherapeutic treatment and we have determined that depletion of these immunosuppressive cells in vitro can restore important T cell effector functions.

Importantly and relevant to the current application, our preliminary studies show evidence of decreased frequency of several immunosuppressive cells in vivo (including PD-1+ T cells) 4-6 weeks after sorafenib treatment in some but not all HCC patients. The decrease in PD-1+ T cell frequency following sorafenib therapy correlated strongly with longer patient survival.

Preliminary in vitro data indicate that the immunomodulatory effects of sorafenib are dose-dependent. Specifically, sorafenib at 10 μ M induced activation of nuclear factor of activated T cells (NFAT) NFAT1 and NFAT2 in CD4 and CD8 T cells. Of note, clinically achievable concentrations of sorafenib exceed 15 μ M. NFAT activation was associated with the gain of an anergic phenotype (gain of PD-1 expression, loss of CD25 expression in CD4 and CD8 T cells and loss of CD8 expression in effector cells). NFAT activation was irreversible upon SOR removal and occurred within a narrow window of activation (between 5 and 10 μ M), demonstrating the threshold of the immunosuppressive action is well above the reported IC50 of sorafenib. In addition to our work, other studies have shown that elevated programmed cell death 1 ligand 1 (PD-L1) expression in HCC is significantly associated with tumor aggressiveness and enhanced risk for postoperative recurrence.(6) Targeted blockade of the PD-L1/PD-1 pathway could facilitate hepatitis virus clearance.(9)

In a Phase 1/2 trial (LBA101) nivolumab another anti-PD-1 antibody showed safety in 47 patients and a response rate of 19%. Although 68% of those patients had received prior sorafenib, no difference was seen in benefit from anti-PD-1 therapy. Based on our work, prior SOR may influence immunosuppressive phenotype and impact patient outcomes.(10)

2.3 Pembrolizumab

Pembrolizumab is a potent and highly selective humanized monoclonal antibody (mAb) of the IgG4/kappa isotype designed to directly block the interaction between PD-1 and its ligands, PD-L1 and PD-L2. Pembrolizumab is approved in the US for the treatment of patients with advanced/ metastatic melanoma, NSCLC, and HNSCC.

To-date, pembrolizumab is being used as both a monotherapy, and in combination with other therapies, in more than 30 tumor types.

Preclinical Studies with Pembrolizumab

A detailed discussion of the preclinical pharmacology, pharmacokinetics, and toxicology of pembrolizumab can be found in the Investigator's Brochure v11.

2.4 Correlative Studies

- **PD-L1/L2 Expression**

The current understanding on whether PD-L1 and PD-L2 status is a biomarker of response is limited, as there are no published data on frequency of PD-L1/L2 expression in western populations and there is no uniformly accepted readily available validated assay. To test the hypothesis that PDL-1/L2 status correlates with outcome, pre-and post-treatment formalin-fixed, paraffin-embedded (FFPE) tissue will be evaluated using the validated assay by Merck. As ligand status was not tested in all patients in prior trials and, some PD-L1 / L2 + patients failed to respond, we as yet do not know if this should be an exclusion criterion. In patients whose tumors are PD-L1 / L2 positive before therapy commences and they do NOT respond to combination treatment, then an optional second biopsy will be performed to test our hypothesis that there may be a change in their PD-L1 / -L2 expression status.

- **Immune Biomarkers**

Determining immune marker changes that can predict clinical benefit and toxicities (as some of them may have an immune basis) would be valuable to the clinician. To this end we propose to address our hypothesis that sorafenib+anti-PD-1 treatment will diminish checkpoint blockade and the accumulation of immunosuppressive networks in advanced stage HCC patients and thereby restore beneficial cytotoxic anti-tumor function in effector T cells. We will assess the alteration in the frequency and phenotype of immunosuppressive cells prior to treatment and, importantly, at three additional time points after commencement of the combination. In addition, the activity of the NFAT transcription factor which regulates PD-1 expression in these cells will be assessed. A longitudinal study of this nature is ideal to determine the kinetics and maintenance of sorafenib and anti-PD1 mediated immunomodulation.

Baseline levels of immunosuppressive cells and the functional activity of effector T cells as measured by NFAT activity, proliferative capacity and IFN-gamma and granzyme B production will be correlated with OS to determine whether these could serve as biomarkers and identify patients most likely to benefit from the combination therapy.

- **Immune-Mediated Adverse Events:**

A number of serious AEs observed with pembrolizumab are immune-mediated pneumonitis, thyroiditis, renal insufficiency and transaminitis, and many of these are also seen with sorafenib therapy, although the mechanism for these effects remains unknown. We propose to assess TSH and anti-thyroid antibodies at baseline and while patients are on therapy and correlate them with immune suppression.

- **Immunomodulatory Effects of Sorafenib/Pembrolizumab:**

Chronic hepatitis B and C virus infection are known risk factors for the development of cirrhosis and HCC. Since immune modulation could affect viral replication; resulting in potential liver function abnormalities or radiographic changes in the liver, viral titers for Hepatitis B and Hepatitis C (Hepatitis B Surface Antigen (HBsAg) and/or detectable HBV DNA and, Hepatitis C Antibody anti-HCV Ab) and detectable HCV RNA) will be measured at baseline (and as clinically indicated in patients who have elevated baseline titers) and at every 12 weeks from the start of combination therapy (C1D1) to assess possible effects on outcome.

- **Pharmacodynamic Markers**

In our studies we have seen PK/PD modelling of a pharmacodynamics marker solubleVEGFR2 along with drug exposure to predict clinical response in HCC patients receiving sunitinib and propose to test the hypothesis that this model could be used to predict response to this sorafenib combination.

2.5 Rationale

Inflammation and immune dysfunction are hallmarks of HCC. Our studies show that HCC is associated with increased levels of PD-1+ cells. Immunomodulation can partially restore effector function, suggesting that targeted blockade of PD-1 may be of clinical benefit in HCC.

Importantly, the preliminary evidence that sorafenib dose-dependently affects PD-1 expression in T cells supports the concept of combining sorafenib with a PD-1 targeting drug. There remains a great need for rationally selected, noninvasive, prospectively validated biomarkers with the potential to provide mechanistic information on how the drug/combination worked or why it did not work. The studies we propose meet all these needs.

Pembrolizumab is a humanized IgG4 monoclonal antibody (mAb) which binds PD-1, and thus, inhibits cognate interaction with PD-L1 and PD-L2. PD-1 is an immune-checkpoint receptor expressed on T cells and high levels of PD-L1 expression are correlated with poor prognosis and survival in HCC. There is an urgent unmet need for novel therapies for patients with HCC that build on the backbone of the approved agent sorafenib.

Successful completion of this study will significantly impact the development of pembrolizumab, the field of HCC research and biomarker development in oncology as a whole. In addition to the much-needed clinical impact this combination will have, new knowledge on the immunomodulatory effects of sorafenib alone, and how anti-PD-1 therapy augments efficacy will be gained from the biomarker work. In oncology biomarker research, the paradigm has always been prediction of response to the therapy being studied: having a marker that would allow for rational selection or prediction of benefit of a combination therapy, would be a major paradigm shift.

3.0 Inclusion and Exclusion Criteria

To be included in this study, participants must meet the criteria listed in Section 3.1.

Participants will be excluded from this study following the criteria listed in Section 3.2.

3.1 Inclusion Criteria**INVESTIGATOR STUDY ELIGIBILITY VERIFICATION FORM:
INCLUSION CRITERIA****Participant Name: (Multi-site use participant initials):** _____**Medical Record No.: (Multi-site use participant ID):** _____**Title: A Phase Ib/ II Study of Sorafenib and Pembrolizumab in Advanced Hepatocellular Cancer (HCC).**

INCLUSION CRITERIA				
Yes	No	N/A	All answers must be "Yes" or "N/A" for participant enrollment.	Date
			1. Age \geq 18 years.	
			2. Participant must have histologically or radiographically confirmed HCC that is advanced or metastatic and if archival tissue is available , have archival tissue submitted for PD-L1, PD-L2 testing.	
			3. Participants with measurable disease that has progressed are eligible if prior surgery or locoregional therapy occurred $>$ 28 days prior to enrollment.	
			4. Have an ECOG Performance Status of 0-1 (Karnofsky \geq 60%). Refer to Appendix B.	
			5. Child-Pugh Class-A liver function. Refer to Appendix C.	
			6. Have the following clinical laboratory values: 
 • ANC \geq 1,500/ mcL • Hemoglobin \geq 8.5 g/dL • Platelets \geq 75,000/ mcL • total bilirubin \leq 2.0 mg/dL • AST and ALT \leq 5 X ULN • Serum Creatinine \leq 1.5 X ULN or Creatinine clearance $>$ 50 mL/ minute if serum creatinine is elevated above 1.5 X ULN 	
			7. Have measurable disease per RECIST 1.1 criteria present.	
			8. Ability to swallow and retain oral medication.	
			9. Participants of child-bearing potential must agree to use adequate contraceptive methods (e.g., hormonal or barrier method of birth control; abstinence) prior to study entry. Should a woman become pregnant or suspect she is pregnant while she or her partner is participating in this study, she should inform her treating physician immediately.	
			10. Participant must understand the investigational nature of this study and sign an Independent Ethics Committee/Institutional Review Board approved written informed consent form prior to receiving any study related procedure.	

Roswell Park Protocol No.: I 35316

INCLUSION CRITERIA				
Yes	No	N/A	All answers must be "Yes" or "N/A" for participant enrollment.	Date
			11. Participants with past or ongoing hepatitis C virus (HCV) infection will be eligible for the study. The treated participants must have completed their treatment at least 1 month prior to starting study intervention.	
			12. Participants with controlled hepatitis B will be eligible as long as they meet the following criteria: 
Antiviral therapy for HBV must be given for at least 12 weeks and HBV viral load must be less than 100 IU/mL prior to first dose of study drug. Participants on active HBV therapy with viral loads under 100 IU/mL should stay on the same therapy throughout study treatment.Participants who are anti-HBc (+), negative for Hepatitis B surface antigen (HBsAg), and negative or positive for anti-HBs, and who have an HBV viral load under 100 IU/mL, do not require HBV anti-viral prophylaxis.	

Investigator Signature: _____ Date: _____

Printed Name of Investigator: _____

Roswell Park Protocol No.: I 35316

3.2 Exclusion Criteria**INVESTIGATOR STUDY ELIGIBILITY VERIFICATION FORM:
EXCLUSION CRITERIA****Participant Name: (Multi-site use participant initials):** _____**Medical Record No.: (Multi-site use participant ID):** _____**Title: A Phase Ib/ II Study of Sorafenib and Pembrolizumab in Advanced Hepatocellular Cancer (HCC).**

EXCLUSION CRITERIA				
Yes	No	N/A	All answers must be "No" or "N/A" for participant enrollment.	Date
			1. One prior line of therapy that may include a PDL1 blocker allowed, no prior sorafenib or PD1 blocker allowed.	
			2. Participants who have had radiotherapy or chemotherapy within 4 weeks (6 weeks for nitrosoureas or mitomycin C) prior to entering the study or those who have not recovered from adverse events due to agents administered more than 4 weeks earlier.	
			3. Any evidence of bleeding diathesis (patients on therapeutic warfarin or heparin will be excluded).	
			4. Participants with a history of variceal bleed within 6 months prior to enrollment.	
			5. Known HIV-positive participants (even if on combination retrovirals, participant will be excluded because of the expected pharmacokinetic drug interactions and unknown safety of anti PD-1 therapy in that patient population).	
			6. Participants with chronic autoimmune disease.	
			7. Participants with known brain metastases should be excluded from this clinical trial because of their poor prognosis and because they often develop progressive neurologic dysfunction that would confound the evaluation of neurologic and other adverse events.	
			8. Uncontrolled intercurrent illness including, but not limited to, ongoing or active infection, symptomatic congestive heart failure, unstable angina pectoris, cardiac arrhythmia, or psychiatric illness/social situations that would limit compliance with study requirements.	
			9. Has known history of, or any evidence of active, non-infectious pneumonitis.	
			10. Pregnant or nursing female participants.	
			11. Unwilling or unable to follow protocol requirements.	
			12. Any condition which in the Investigator's opinion deems the participant an unsuitable candidate to receive study drug.	
			13. Received a live vaccine within 30 days prior to start of study treatment.	

Participant meets all entry criteria: Yes No

If "NO", do not enroll participant in study.

Roswell Park Protocol No.: I 35316

Investigator Signature: _____ **Date:** _____

Printed Name of Investigator: _____

Roswell Park Protocol No.: I 35316

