10.2 Pembrolizumab

Starting with Cycle 1, treatment with pembrolizumab will be administered on Day 1 of each 3-week treatment cycle, after all procedures and assessments have been completed (as detailed on the Schedule of Procedures: Appendix E).

Pembrolizumab will be administered at a fixed dose of 200 mg, using a 30-minute IV infusion. Sites should make every effort to target infusion timing to be as close to 30 minutes as possible. However, given the variability of infusion pumps from site to site, a window between -5 minutes and + 10 minutes is permitted (i.e., infusion time is 30 minutes -5 min and + 10 min).

The Pharmacy Manual contains specific instructions for the preparation of the pembrolizumab infusion and administration of infusion solution.

Toxicities will be assessed upon completion of the first 6 evaluable patients to see if any higher than anticipated occurrence of sorafenib toxicity is seen due to the addition of pembrolizumab.

Reported adverse events (AEs) and potential risks are described in Section 13. Appropriate dose modifications are described in Table 1 (see **Appendix F**).

Pembrolizumab Dose Modifications

Adverse events (both non-serious and serious) associated with pembrolizumab exposure may represent an immunologic etiology. These adverse events may occur shortly after the first dose or several months after the last dose of treatment. Pembrolizumab must be withheld for drug-related toxicities and severe or life-threatening AEs as per Table 1 (**Appendix F**).

Dosing interruptions are permitted in the case of medical / surgical events or logistical reasons not related to study therapy (e.g., elective surgery, unrelated medical events, patient vacation, and/or holidays). Participants should be placed back on study therapy within 3 weeks of the scheduled interruption. The reason for interruption should be documented in the patient's study record.

Management and dose modifications associated with the above AEs are outlined in **Appendix F**.

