10.3 General Concomitant Medications

Medications or vaccinations specifically prohibited in the exclusion criteria are not allowed during the ongoing trial. If there is a clinical indication for one of these or other medications or vaccinations specifically prohibited during the trial, discontinuation from trial therapy or vaccination may be required. The final decision on any supportive therapy or vaccination rests with the primary investigator and/or the subject's primary physician.

Acceptable Concomitant Medications

All treatments that the investigator considers necessary for a patient's welfare may be administered at the discretion of the investigator in keeping with the community standards of medical care. All concomitant medication will be recorded on the case report form (CRF) including all prescription, over-the-counter (OTC), herbal supplements, and IV medications and fluids. If changes occur during the trial period, documentation of drug dosage, frequency, route, and date may also be included on the CRF.

All concomitant medications received within 28 days before the first dose of trial treatment and 30 days after the last dose of trial treatment should be recorded. Concomitant medications

Roswell Park Protocol No.: I 35316

administered after 30 days after the last dose of trial treatment should be recorded for SAEs and ECIs as defined in Section 17.0.

Prohibited Concomitant Medications

Patients are prohibited from receiving the following therapies during the Baseline and Treatment Phase of this study:

- Antineoplastic systemic chemotherapy or biological therapy
- Immunotherapy not specified in this protocol
- Chemotherapy not specified in this protocol
- Investigational agents other than pembrolizumab
- Radiation therapy
 - *Note:* Radiation therapy to a symptomatic solitary lesion or to the brain may be allowed at the investigator's discretion.
- Live vaccines within 30 days prior to the first dose of trial treatment and while participating in the trial. Examples of live vaccines include, but are not limited to, the following: measles, mumps, rubella, varicella/zoster, yellow fever, rabies, BCG, and typhoid vaccine.
- Anti-viral medications for treatment of hepatitis C while receiving combination therapy
 - *Note:* Patients may continue on anti-viral medication for hepatitis C during the 4-week sorafenib-only therapy.

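### A prior PD-L1 blocker is allowed with no stated interval before entry, so the baseline scan can follow the last dose by days and shrinkage from the earlier drug could count as a response to the combination

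*Combined protocol and SAP*

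**What the plan says.** Section 3.2, exclusion 1, reads: "One prior line of therapy that may include a PDL1 blocker allowed, no prior sorafenib or PD1 blocker allowed". Exclusion 2 then bars "Participants who have had radiotherapy or chemotherapy within 4 weeks (6 weeks for nitrosoureas or mitomycin C) prior to entering the study", together with "those who have not recovered from adverse events due to agents administered more than 4 weeks earlier". Inclusion 3 in Section 3.1 sets more than 28 days for other prior treatment: "Participants with measurable disease that has progressed are eligible if prior surgery or locoregional therapy occurred" before that limit. It is the only criterion that mentions progression, and it concerns surgery and locoregional therapy.

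Section 10.3 opens its prohibited list with "Patients are prohibited from receiving the following therapies during the Baseline and Treatment Phase of this study". The list includes "Immunotherapy not specified in this protocol" as an item separate from chemotherapy, and it also names biological therapy. Appendix E, footnote 1, gives Baseline an upper limit of 28 days before sorafenib starts and no minimum.

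Section 10.1 puts patients on sorafenib alone for 4 to 6 weeks after enrollment. Section 8.0 counts partial or complete response by irRECIST within 6 months of starting the combination. Appendix H measures partial response as a fall of at least 30% in tumor burden from baseline. Section 19.1 declares the treatment effective with 4 or more responders among 27 evaluable patients.

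**The concern.** For chemotherapy, the two halves of exclusion 2 cover all time before entry: a recent dose excludes the patient, and an older dose requires recovery. For a PD-L1 blocker given less than 4 weeks before entry, neither half applies. Reading the word chemotherapy to include a PD-L1 blocker does not fit Section 10.3, which lists the classes separately.

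The main exposure is the reference scan. It is taken at Baseline, before sorafenib, and the only limit on a PD-L1 dose at that point is the Section 10.3 prohibition, which runs for a Baseline period of no minimum length. If a tumor is still shrinking from the earlier drug, the shrinkage is measured against that scan and credited to sorafenib plus pembrolizumab. The trial has a single arm and is decided by 4 responders, so one misattributed response matters. Section 19 plans no analysis by prior PD-L1 exposure that would show whether this happened.

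**Working it through.** **1. Is there an interval from the last PD-L1 dose?** The provisions side by side:

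| Provision | Reaches a PD-L1 blocker? |
|---|---|
| Exclusion 2, interval | No; radiotherapy and chemotherapy only |
| Exclusion 2, recovery clause | Only if given more than 4 weeks earlier |
| Inclusion 3, more than 28 days | No; surgery and locoregional therapy only |
| Section 10.3, prohibited during Baseline | Yes, but Baseline has no minimum length |
| Section 10.1, sorafenib lead-in | Delays pembrolizumab by 4 to 6 weeks, not entry or the scan |

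So pembrolizumab starts about 4 weeks or more after any PD-L1 dose, while the baseline scan may follow one by days.

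**2. The plan's own design figure.** Inputs from Section 19.1: n = 27, success if X ≥ 4, null rate 0.05, alternative 0.20.

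The formula is P(X ≥ 4) = 1 − Σ C(27, x) pˣ (1 − p)²⁷⁻ˣ, summed over x = 0 to 3.

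- At p = 0.05: 1 − (0.2503 + 0.3558 + 0.2434 + 0.1068) = 0.0437, within the stated 5%.
- At p = 0.20: 0.818, meeting the stated 80%.

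The design reproduces. There is little slack: the first figure passes 0.05 once the average null response rate exceeds about 5.22%.

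**3. Effect of carry-over under assumed inputs.** Let k of the 27 have prior PD-L1 exposure, each with an extra chance q of a response due to the earlier drug. Neither k nor q is in the documents. An exposed patient responds with probability 1 − 0.95(1 − q), and the others with 0.05. The number of responders is the sum of the two binomial groups, and the entry is P(total ≥ 4):

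| k | q = 0.02 | q = 0.05 | q = 0.10 |
|---|---|---|---|
| 3 | 0.050 | 0.059 | 0.076 |
| 5 | 0.054 | 0.071 | 0.104 |
| 8 | 0.060 | 0.090 | 0.154 |

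**4. Two bounding cases.**

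- If one counted response is certainly carry-over, the rule becomes at least 3 of the other 26: 1 − (0.2635 + 0.3606 + 0.2372) = 0.139. With two it is at least 2 of 25, which gives 0.358.
- In the other direction, if exposed patients could not respond at all, the rule becomes at least 4 of 27 − k: 0.030 for k = 3, 0.022 for k = 5 and 0.013 for k = 8.

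**The case against.** The other side has a good deal of force, and several stronger readings should be set aside.

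- A reader might infer that pembrolizumab can start days after a PD-L1 dose. It cannot. The Section 10.3 prohibition and the lead-in separate them by about 4 weeks or more, and the window for dose-limiting toxicity opens only with the first combination cycle.
- A reader might infer that toxicity from a recent PD-L1 blocker goes uncaught. Some of it is caught whatever the timing: exclusion 9 covers pneumonitis, exclusions 8 and 12 cover uncontrolled illness and investigator judgment, and inclusion 6 sets liver and renal limits. These do not reach toxicity that first appears after entry. In the lead-in cohort, carry-over toxicity would make the combination look worse. The stopping rule also counts only unexpected events, so recognized immune events may not trigger it.
- A reader might cite Section 10.2, "These adverse events may occur shortly after the first dose or several months after the last dose of treatment", as proof of late response. That sentence concerns adverse events with pembrolizumab. It says nothing about response, or about a stopped PD-L1 blocker.
- A reader might quote 13.9% or 35.8% as the type I error. Those figures assume that one or two carry-over responders are certain, which nothing in the documents supports.
- The direction is not settled. Patients who failed a PD-L1 blocker may respond less often, and the probability of a false success then falls.
- An interval may not remove an effect that lasts for months, and the 6-month response window would still capture it.

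What survives is the missing interval, the unprotected baseline scan, the absence of a progression requirement on that line, and the lack of any analysis that would show the effect.

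**Conclusion.** The gap is real and worth closing, but it is an eligibility and attribution gap. No stated design figure is wrong. As written, the criteria allow the irRECIST reference scan to be taken days after a PD-L1 dose, in a trial that 4 responders decide.

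Its size cannot be known from the documents. With 3 to 8 of 27 exposed and an extra response chance of 2% to 10% each, the probability of a false success at a 5% background rate is 0.050 to 0.154, against 0.044 as designed. That range rests on assumed exposure and assumed carry-over, and on exposed patients otherwise responding at the same 5%. If few such patients enroll, or if they respond less often, the effect is negligible or reversed. This is an inexpensive improvement that should be made. It is not a flaw that invalidates the design.

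**What to change.** Reconcile exclusions 1 and 2 and Section 10.3 so that the pre-entry interval and the recovery condition apply to every prior systemic anticancer agent, PD-L1 blockers included. The length is for the sponsor to set. State whether it runs to enrollment or to the baseline scan, since the scan can come first.

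Record the date of the last PD-L1 dose and whether the disease had progressed on that line. Add to Section 19 a descriptive report of the response rate and of first-cycle toxicity with and without PD-L1-exposed patients.

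The cost is eligibility wording, two data items and one table. The sample size, threshold, type I error and power stay as they are. The downside is that a few pretreated patients wait before entry. An interval reduces late carry-over but may not remove it, so the split report is needed as well.
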